6.5.1 Data Collection and Follow-up for Withdrawn Subjects

We will attempt to have one final visit or contact to follow up regarding adverse events for participants who withdraw prior to the 30 day follow up visit. During this contact they will be asked for permission to have the study team look into their survival status via their electronic medical records and publicly available means.

7 Statistical Plan

Primary Endpoint

The primary endpoint of this study will be the change in PaO₂/FiO₂ ratio at 0, 24, 48, and 72 hours after implementation of core warming of ventilated patients. This endpoint will be compared between patients receiving core warming and those randomized to undergo standard care (standard temperature management, with or without antipyretics as needed).

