3.1 General Design

This is a small scale pilot study to evaluate if core warming improves respiratory physiology of mechanically ventilated patients with COVID-19, allowing earlier weaning from ventilation, and greater overall survival. This prospective, randomized study will include 22 patients diagnosed with COVID-19, and undergoing mechanical ventilation for the treatment of respiratory failure. Patients will be randomized in a 1:1 fashion with 11 patients (Group A) randomized to undergo core warming, and the other 11 patients (Group B) serving as the control group who will not have the ensoETM device used. Patients randomized to Group A will have core warming initiated in the ICU or other clinical environment in which they are being treated after enrollment and provision of informed consent from appropriate surrogate or legally authorized representative.

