4.3 Subject Recruitment

Subjects will be recruited from the ICU or other clinical environment in which they are being treated (Emergency Department, step-down unit, etc.). Patients will be identified by the PI or other study investigators/coordinators as available. All patients without a DNR order with a diagnosis of COVID-19 and meeting inclusion criteria will be eligible for screening for any exclusion criteria. The study team will pre-screen the potential subject's EMR, to assess all other inclusion/exclusion criteria, prior to approaching the patient and/or their surrogate / legally authorized representative about study participation. Written informed consent for the research study will be obtained from patient's surrogate or legally authorized representative prior to enrollment. If a patient enrolled in the study gains the capacity to consent for him/herself while the study is in progress, the patient will be approached by a study team member and the consent document will be presented directly to the patient. All questions the patient might have will be answered. The patient will be given the opportunity to either withdraw from the study or sign the consent form. The patient will be informed that his or her decision to withdraw from the study will not affect his or her medical care

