4.5 Total Number of Subjects and Sites

Recruitment will end when 22 participants are randomized.

5 Study Intervention

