6.5 Subject Withdrawal

Subjects may withdraw from the study at any time without impact to their care. They may also be discontinued from the study at the discretion of the Investigator for lack of adherence to study procedures or visit schedules, AEs, or should it become clinically necessary to deviate from the study protocol during the course of the study. The Investigator may also withdraw subjects who violate the study plan, or to protect the subject for reasons of safety or for administrative reasons. It will be documented whether or not each subject completes the clinical study. We will attempt to have one final visit or contact to follow up regarding adverse events for participants who withdraw prior to the 30 day follow up visit.

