7.2 Sample Size and Power Determination

Based on a prior study in patients with sepsis, a maximum temperature of 38.3°C to 39.4°C was associated with survival (aHR 0.61 [95% CI, 0.39-0.99]).[29] However, the effect of warming specific to COVID-19 patients remains uncertain, and as such, we are unable to accurately perform a power calculation for this pilot study. We believe that a total of 10 patients for each group will be required to yield the necessary pilot data to make an appropriate conclusion regarding the potential utility of core warming in reducing viral shedding, improving pulmonary physiology, reducing mechanical ventilation duration, and increasing patient survival. It is anticipated that data from this pilot study can be used for planning future larger studies.

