9.1 Confidentiality

Information about study subjects will be kept confidential and managed according to the requirements of the Health Insurance Portability and Accountability Act of 1996 (HIPAA). Those regulations require a signed subject authorization informing the subject of the following:

- What protected health information (PHI) will be collected from subjects in this study
- Who will have access to that information and why
- Who will use or disclose that information
- The rights of a research subject to revoke their authorization for use of their PHI.

In the event that a subject revokes authorization to collect or use PHI, the investigator, by regulation, retains the ability to use all information collected prior to the revocation of subject authorization. For subjects that have revoked authorization to collect or use PHI, attempts should be made to obtain permission to collect at least vital status (i.e. that the subject is alive) at the end of their scheduled study period.

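### Survival status of withdrawn patients depends on permission sought at one attempted later contact, with no fallback, so Day 30 mortality may be missing in a way that depends on outcome

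*Combined protocol and SAP*

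**What the plan says.** Section 6.5.1 is the protocol's rule for follow-up after withdrawal. The team will try once to reach the participant about adverse events, and "During this contact they will be asked for permission to have the study team look into their survival status", using medical records and public sources.

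Three other sections bear on who falls under that rule:

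- Section 6.5 lets participants leave, and adds: "The Investigator may also withdraw subjects who violate the study plan, or to protect the subject for reasons of safety or for administrative reasons".
- Section 4.3 covers patients who recover capacity after a surrogate enrolled them: "The patient will be given the opportunity to either withdraw from the study or sign the consent form".
- Section 9.1 covers revoked privacy authorization: "attempts should be made to obtain permission to collect at least vital status (i.e. that the subject is alive", with data gathered before revocation still usable.

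Mortality is a secondary endpoint (Sections 3.2.2 and 7.1), and survival is part of the stated purpose (Section 2). Section 7.4 restricts analysis to patients who were enrolled and randomized and who also completed the study. No rule for missing mortality data is given.

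**The concern.** These patients are ventilated and are enrolled through a surrogate or legally authorized representative. A rule that waits for a later contact and then asks the participant works best for those who are alive and awake. The text is silent on a patient who has died or is still sedated by then, and on whether the surrogate may reply. Whether a death is known can then depend on whether it has happened.

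Two features add to this. When the investigator withdraws a patient, neither patient nor surrogate has retracted anything. Yet Section 6.5 uses the word withdraw and Section 6.5.1 is headed for withdrawn subjects, so a coordinator could think that new permission is needed. Separately, only recovering patients face the choice in Section 4.3 between signing and withdrawing, so losses there would be tied to good outcome and would pull the estimate the other way.

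What is at stake is the descriptive mortality estimate, which Section 7.2 expects to help in planning larger studies.

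**Working it through.** **Inputs.** Section 4.5: "Recruitment will end when 22 participants are randomized". Section 3.1: "Patients will be randomized in a 1:1 fashion with 11 patients (Group A) randomized to undergo core warming". Check: 2 × 11 = 22, which agrees. Section 7.2 instead gives 10 per group (2 × 10 = 20), a separate inconsistency; I use 11. The same section says "we are unable to accurately perform a power calculation for this pilot study". No withdrawal rate, control mortality or dropout allowance is stated, so there is no plan figure on this point to reproduce.

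**Step 1: what the text settles, by route out of the study.**

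| Route | Is Day 30 vital status settled? |
|---|---|
| Withdraws, is reached, agrees (6.5.1) | Yes, from records and public sources |
| Withdraws, is reached, refuses (6.5.1) | No rule stated |
| Withdraws, has died or cannot answer (6.5.1) | No fallback; surrogate not named |
| Withdrawn by the investigator (6.5) | Unclear whether 6.5.1 or the existing consent governs |
| Recovers capacity and declines (4.3) | Can be asked, but only at the later contact |

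**Step 2: bounds.** With d known deaths and u unknown among 11, mortality lies between d/11 and (d + u)/11, a width of u/11. One unknown gives 1/11 = 9.1 points, two give 18.2 and three give 27.3. This needs no assumption about rates.

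**Step 3: illustrative bias (death counts assumed).** If w of d deaths are missed and those patients are excluded, observed mortality is (d − w)/(11 − w) instead of d/11.

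- d = 4, w = 1: 3/10 = 30.0% against 4/11 = 36.4%, a shift of 6.4 points.
- d = 4, w = 2: 2/9 = 22.2% against 36.4%, a shift of 14.1 points.
- For d from 3 to 7, the shift is 3.6 to 7.3 points with one missed death and 8.1 to 16.2 with two.
- If missed deaths are counted as alive, the shift is w/11: 9.1 or 18.2 points.

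**Step 4: the same shift from Section 7.4.** Take d = 4, with two of those deaths in withdrawn patients and both fully known. Under a completers-only population those two patients leave numerator and denominator, giving (4 − 2)/(11 − 2) = 2/9 again. In all randomized patients with known status, the result is 4/11. Ascertainment alone therefore does not restore the estimate.

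**Step 5: how often (rates assumed).** Let q be the probability of withdrawal and p the probability of death given withdrawal, with every such death missed. Expected missed deaths are 22qp, and the chance of at least one is 1 − (1 − qp)^22.

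- q = 5%, p = 30%: 0.33 deaths; 1 − 0.985^22 = 28%.
- q = 20%, p = 50%: 2.2 deaths; 1 − 0.90^22 = 90%.

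**Step 6: what the comparison could show anyway.** Section 7.2 cites an adjusted hazard ratio of 0.61 from a sepsis cohort, without using it for design. At two-sided 0.05 (assumed), 80% power for that ratio needs 129 events by the Schoenfeld formula. If all 22 patients died, power would be 21%.

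**The case against.** A reader might infer that survival may be looked up only with this permission, that withdrawn patients who die first are never counted, and that this applies to anyone who leaves. The documents do not say so. Section 6.5.1 says permission will be sought; it does not bar other ways of learning of a death. Section 8.2 records adverse events from consent through 30 days, and a fatal event is serious under Section 8.1.2. Section 4.4 foresees chart review. The surrogate who consented may be reachable. Nothing says that a patient discontinued by the investigator loses follow-up.

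These points stand against the stronger reading, but they do not close the gap. Section 8.2 gathers events at contacts with the subject and does not say that collection continues after withdrawal. Section 6.5.1 neither names nor excludes the surrogate, and the wording of 6.5 and 6.5.1 leaves investigator withdrawals ambiguous.

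A reader might also infer a bias in favour of Group A, since only that arm has the device. An excess of safety withdrawals there is plausible but assumed, and Section 6.3 sends repeated device malfunction to standard care, not out of the study. Losses under Section 4.3 would act in the opposite direction, so the net sign is unknown.

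The wording about being alive in Section 9.1 is only a loose gloss: checking it also reveals death. The consent form was not available for this review and may already cover record follow-up. Seeking permission after a true withdrawal of consent is an ordinary safeguard; the difficulty lies in when and of whom it is asked.

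**Conclusion.** The concern holds as a risk: as written, Day 30 vital status for withdrawn patients may be missing in a way that depends on outcome, and Section 7.4 can discard these patients even when their status is known. The firm size is 9.1 points of added uncertainty in an arm's mortality for each unknown status. The 6.4- and 14.1-point shifts assume four deaths in an arm with one or two missed, and the 28% to 90% range assumes the rates in Step 5; none of these is a forecast. Because the endpoint is secondary and unpowered, the harm is to a descriptive pilot estimate, not to a confirmatory test. Severity is low to moderate.

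**What to change.** - **Section 6.5.1, investigator-initiated discontinuation:** state that Day 30 vital status and the ventilation end date are taken from the chart under the existing consent, unless that consent is withdrawn.
- **Section 6.5.1, withdrawal by patient or surrogate:** ask whoever is withdrawing, at that moment, whether chart and vital-status follow-up to Day 30 may continue, and record the answer on the withdrawal form. In Section 4.3, offer the same option to a patient who recovers capacity.
- **Section 7.4:** analyse mortality in all randomized patients by assigned arm, and report best-case and worst-case bounds for any unknown status.

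The third change is needed with the first two: an all-randomized analysis needs the status to be collected, and collected status is of no use if completers alone are analysed. The cost is a protocol amendment with IRB review, a check of the consent form for matching wording, and one item on a form. Some patients or surrogates may still refuse; their status then stays unknown and is carried by the bounds.

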Objectives	
Primary:
 
 • Determine the change in PaO₂/FiO₂ ratio at 0, 24, 48, and 72 hours after implementation of core warming of ventilated patients, and compare this change to patients undergoing standard care. 
Secondary:
 
 • Determine the change in viral load measured in nasopharyngeal swab by Cycle Threshold at 0, 24, 48, and 72 hours after implementation of core warming of ventilated patients, and compare this change to patients undergoing standard care. • Measure the impact of core warming on duration of mechanical ventilation. • Determine impact of core warming on patient mortality.
Number of Participants	22
Length of Participation	72 hour intervention phase; 30 day follow up

Inclusion Criteria	
 1. Patients above the age of 18 years old. 2. Patients with the diagnosis of COVID-19 requiring mechanical ventilation. 3. Patient maximum baseline temperature (within previous 12 hours) < 38.3°C. 4. Patients must have surrogate or legally authorized representative able to understand and critically review the informed consent form.
Exclusion Criteria	
 1. Patients without surrogate or legally authorized representative able to provide informed consent. 2. Patients with contraindication to core warming using an esophageal core warming device. 3. Patients known to be pregnant. 4. Patients with <40 kg of body mass. 5. Patients with DNR status. 6. Patients with acute stroke, post-cardiac arrest, or multiple sclerosis.
Investigational Device	Attune Medical esophageal heat transfer device – ensoETM. Used as indicated for patient temperature management.
Duration of administration	72 hours
Reference therapy	Standard temperature management as routine at study site
Statistical Methodology	A total of 11 patients for each group will be required to yield the necessary pilot data regarding the feasibility and effect of core warming on viral load and ventilation requirements.
Safety Evaluations	Standard adverse event monitoring (device is in widespread use for patient warming and cooling).
Data and Safety Monitoring Plan	The PI and research team will be responsible for data and safety monitoring.

This study will be conducted in full accordance with all applicable study site research policies and procedures and all applicable federal and state laws and regulations.

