3.1.4 Allocation to Interventional Group

The randomization algorithm will be built into the electronic data capture system, Redcap, which will be used to collect data in the study. Once the randomization form is entered into the system and saved, the back end algorithm will run and a participant will be assigned an arm corresponding to either study device (Group A – Core warming) or standard of care (Group B – Control). Patients will undergo randomization after being enrolled into the study and prior to the placement of the core warming device. Randomization will be performed in a 1:1 fashion and maintained on the limited access, encrypted, Redcap database.

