3.2 Study Endpoints

The purpose of the proposed pilot study is to determine if core warming reduces the severity of acute respiratory distress syndrome as measured by PaO₂/FiO₂ ratio 72 hours after initiation.

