3.2.1 Primary Study Endpoints

The primary endpoint of this study will be:

1. PaO₂/FiO₂ ratio at 0, 24, 48, and 72 hours after initiation of core warming

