6.1 Pre-Screening

Patients will be screened within 24 hours prior to the Baseline/Randomization timepoint to determine potential eligibility.

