7.3.2 Interim Safety Analysis

All subjects entered into the study and randomized at the baseline timepoint will have detailed information collected on adverse events for the overall study safety analysis. An interim safety analysis will be performed after the first 10 subjects are enrolled in the trial. At this time the safety and tolerability of the study device will be assessed and if deemed safe and appropriate, enrollment will continue to 22 subjects.

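### The primary endpoint is stated as a P/F level in one section and as a change in others, no decisive time is named, and its hours count from a start of core warming that controls never have

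*Combined protocol and SAP*

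**What the plan says.** **Outcome**

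- Section 3.2, the purpose sentence: severity is measured by the PaO2/FiO2 "ratio 72 hours after initiation".
- Section 3.2.1, the numbered primary endpoint: the PaO2/FiO2 "ratio at 0, 24, 48, and 72 hours after initiation of core warming". This is a level, with no mention of change.
- Section 7, Primary Endpoint: the change in the PaO2/FiO2 "ratio at 0, 24, 48, and 72 hours after implementation of core warming of ventilated patients".
- Study Summary and 2.1: the objective is to determine the change at the same four times "and compare this change to patients undergoing standard care".

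**Clock**

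- Each of these statements counts from initiation or implementation; all but the short sentence in 3.2 name core warming outright. Viral load is timed the same way (Study Summary, 2.2, 3.2.2, 7.1).
- Section 3.1 describes 11 patients "serving as the control group who will not have the ensoETM device used".
- Section 3.1.4: "Patients will undergo randomization after being enrolled into the study and prior to the placement of the core warming device". The length of the delay is not given.
- A common origin is named twice, but not for the endpoint. Section 6.1: "Patients will be screened within 24 hours prior to the Baseline/Randomization timepoint to determine potential eligibility". Section 7.3.2 speaks of subjects "randomized at the baseline timepoint".

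**Analysis and readings**

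- Section 7.3 compares continuous variables by t or Mann–Whitney test. It does not say which variable or time is tested, and it names no baseline adjustment.
- The schedule in section 6 has a P/F row marked for Day 0 and Days 1–2, but not for Screening. No column is labelled 72 h. Section 6.2.2 takes the latest blood gas only if routine care produced one.

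**The concern.** Sections 3.2.1 and 7 both define the primary endpoint formally, and they name different variables. In a trial this small, level and change can give noticeably different estimates because chance baseline imbalance is large. If both definitions stay in force, the choice between them, and the choice of decisive time, can be made after the data are seen. Section 7.2 expects the data to support a conclusion on potential utility and to help plan larger studies. A later trial needs one defined effect and its SD.

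The clock raises a separate comparability question. If hours run from device start in the warmed arm and from some unstated moment in controls, the arms may be read at different times since randomization while P/F is moving.

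**Working it through.** **The plan's own figure.** There is none to reproduce. Section 7.2 says a power calculation could not be done, and no alpha, SD or effect is given.

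**Inputs.** From the documents: 11 per arm (3.1; section 7.2 says 10, a separate mismatch). Assumed: two-sided 5%, equal SDs (results are in SD units), approximate normality, complete data, and a correlation r between baseline and 72-h P/F of 0.3 to 0.7.

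**Step 1: how far level and change can differ.** Let L be the difference between arms in mean 72-h P/F, B the difference in mean baseline P/F, and C the difference in mean change.

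C = L − B, so L − C = B.

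Under randomization B has mean 0 and variance 2/11 = 0.182 in SD units.

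- SD of B = √0.182 = 0.426
- Median absolute gap = 0.6745 × 0.426 = 0.288
- P(gap > 0.5 SD) = 2 × [1 − Φ(0.5/0.426)] = 0.241

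These depend on neither the treatment effect nor r.

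**Step 2: how often one t-test is significant and the other is not at 72 h** (100,000 simulated trials per cell).

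| True effect | r = 0.3 | r = 0.5 | r = 0.7 |
|---|---|---|---|
| 0 | 7.8% | 8.4% | 8.8% |
| 0.25 SD | 11.2% | 12.7% | 15.2% |
| 0.5 SD | 20.0% | 23.2% | 30.3% |
| 1 SD | 32.6% | 33.1% | 35.3% |

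Repeat runs agree, with the range at 1 SD reaching 36% in one. In these discordant trials the two estimates point the same way in about 80–92% of cases with no effect and about 99% at 1 SD.

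**Step 3: what baseline adjustment does.** Change is the 72-h value minus baseline. With baseline as a covariate, using change instead of level only lowers the baseline slope by 1. The treatment coefficient is identical, and a numerical check confirmed this.

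95% CI half-widths:

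- Level: t(20) × √(2/11) = 2.086 × 0.426 = 0.889
- Change: t(20) × √[2(1−r) × 2/11]
- ANCOVA: t(19) × √[(1−r²) × (2/11) × (1 + 1/18)]; at r = 0.5, 2.093 × √(0.75 × 0.1818 × 1.0556) = 0.794

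| r | Level | Change | ANCOVA |
|---|---|---|---|
| 0 | 0.889 | 1.258 | 0.917 |
| 0.3 | 0.889 | 1.052 | 0.875 |
| 0.5 | 0.889 | 0.889 | 0.794 |
| 0.7 | 0.889 | 0.689 | 0.655 |
| 0.9 | 0.889 | 0.398 | 0.400 |

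ANCOVA matches level at r = 0.243 and change at r = 0.882. It is narrower than both in between, and the loss outside that range is small.

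**Step 4: the clock.** No calculation is possible, because the delay from randomization to device start is not stated. Setting 3.1, 3.1.4, 6.1 and 7.3.2 beside the endpoint definitions shows that a shared origin exists and that no sentence connects it to hours 0, 24, 48 and 72.

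**The case against.** - **The text leans towards change.** Section 7 and both statements of the objective say change, and 3.2 is only a purpose sentence. Change from hour 0, sampled at four times with 72 h as the target, fits nearly everything except 3.2.1. This stands, so a reader who infers that the primary result is wholly undefined goes too far. Even so, 3.2.1 is a formal definition that says otherwise, and nothing names the decisive time.
- **The clock is mostly labelling.** Randomization and P/F recording share the Day 0 column, and 6.1 and 7.3.2 equate baseline with randomization. This stands in part: one linking sentence would do, but it is absent.
- **The discordance rates describe no decision in the plan.** There is no alpha or decision threshold. This stands. The rates show the scale of the ambiguity under an assumed 5%. They do not show that the two analyses would reach opposite conclusions, since the estimates usually agree in direction.
- **The exact gap needs conditions.** It holds for mean differences in the same patients with both readings. It does not hold for the Mann–Whitney test that 7.3 also allows, and routine-care gases and the completers-only set in 7.4 may leave fewer than 11 per arm. This stands, and the figures are limited accordingly.
- **ANCOVA is a preference.** The unadjusted tests are valid, and naming change from randomization to 72 h would settle level against change without it. This is fair. The case for ANCOVA is that it makes the choice immaterial and usually gains precision, not that 7.3 is wrong.

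**Conclusion.** The point holds as an inconsistency that should be corrected before any data are analysed. The primary endpoint is a level in one formal definition and a change in another, its decisive time is unnamed, and its hours start from an event that only one arm has. The consequence is a gap between estimates that typically reaches about 0.3 SD and exceeds 0.5 SD in roughly a quarter of trials, given 11 per arm, complete data and mean differences. The significance figures rest further on the assumed 5% and the assumed range of r.

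Two other readings are tempting and not supported. One is that the false-positive rate is inflated. Choosing freely between level and change at 72 h would give about 9%, and among both at 24, 48 and 72 h about 22%, but the plan states no alpha, so it breaches no rate of its own. The other is that the 72-h reading is missing from the schedule. The end of Day 2 may be 72 h, so the fault is imprecise labelling.

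**What to change.** - **Study Summary, 2.1, 3.2, 3.2.1 and 7:** state one primary outcome, the P/F ratio at 72 h, with hour 0 as randomization in both arms.
- **Study Summary, 2.2, 3.2.2 and 7.1:** use the same hour 0 for viral load.
- **Section 7.3:** compare the arms by ANCOVA of the 72-h ratio adjusted for baseline P/F, reported as a mean difference with a 95% CI. Make 24 h and 48 h secondary. If residuals are clearly non-normal, report a rank-based analysis as a sensitivity check. A repeated-measures model with the 72-h contrast as primary would also be acceptable.
- **Section 6:** define baseline as the last P/F at or before randomization within a stated window. Label the 72-h reading and give it a window in both arms. Record the device start time. The baseline window matters because the P/F row has no Screening entry and the gas may be old or absent.

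**Cost.** Wording edits and schedule labels, with no extra patients. ANCOVA spends one degree of freedom and loses slightly if r is below about 0.24. An occasional blood gas may not be routine. Warmed patients will have had slightly under 72 h of warming at the reading; an assumed delay of 1 to 12 h would be 1/72 to 12/72, or 1% to 17%.

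**Not settled by this change.** Patients who die or are extubated before 72 h, and the completers-only analysis set in 7.4, need their own rules.
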